6.3.14 Treatment Assignment / Blindedness Questionnaire

Subjects and Investigators will be asked to complete the Treatment Assignment/ Blindedness Questionnaire during the V11 Final visit or Premature Withdrawal Visit. The Blindedness Questionnaire will be used to assess subject's and Investigator's perception of the knowledge of their group assignment to placebo versus active treatment.

7 MANAGEMENT OF ADVERSE EVENTS

7.1 Isradipine Side Effect Profile

Isradipine IR is a dihydropyridine Ca²⁺ channel antagonist that is FDA approved for treatment of hypertension since 1990 (<http://www.drugs.com/pro/isradipine.html>).

The side effect profile of Isradipine IR is related to the primary mechanism of action of the agent as a vasodilator of the vascular smooth muscles and myocardium, and includes hypotension, bradycardia, weakness, and syncope. The most common adverse effect is peripheral edema as reflection of the vasodilatory effect of the agent. The other side effects include angina, asthenia, flushing, heart failure, palpitations, and dizziness. According to the package insert, the adverse effects are usually not serious, dose dependent, and respond well to dose reduction or discontinuation of therapy.

Isradipine has no effect on atrioventricular or sinoatrial conduction. The only absolute contraindications for Isradipine IR are hypersensitivity to dihydropyridine compounds and hypotension defined as systolic blood pressure below 90 mm Hg. Isradipine IR should be used with caution in subjects with bradycardia. Subjects with clinically significant bradycardia will be excluded from the study.

Below is a list of most common potential Isradipine IR related adverse events from the drug package insert (<http://www.drugs.com/pro/isradipine.html>) .(See Table 4 and 5 above for list of adverse events.)

The adverse effects associated with isradipine generally are not serious and respond well to either dosage reduction or discontinuation of therapy. Most adverse effects during isradipine therapy are related to vasodilatory actions and, in many cases, are dose-related.

The most common cardiovascular adverse effect attributed to isradipine therapy is peripheral edema, which is a reflection of the potent vasodilatory effect of isradipine, although it occurs less frequently than with nifedipine. Peripheral edema may be an indicator of worsening congestive heart failure, but it more commonly is due to peripheral vasodilation.

Although calcium-channel blockers are effective in treating angina, worsening of angina has occurred in as many as 10% of patients receiving isradipine for angina pectoris. This effect may be caused by excessive hypotension, coronary steal, or reflex sinus tachycardia (rare with isradipine). In rare cases, myocardial infarction has occurred but could not be attributed solely to the drug and may have been only a reflection of disease progression. Patients with angina should be observed for worsening symptoms when isradipine therapy is begun, particularly if beta-blocker therapy is being withdrawn.

Other common side effects of isradipine, primarily related to vasodilation, include flushing, weakness or asthenia, fatigue, headache, syncope, hypotension, palpitations, dizziness, and lightheadedness.

Less common but potentially serious adverse effects of isradipine include angioedema, dyspnea, wheezing (especially if underlying respiratory disease or pulmonary edema exists), vertigo, and visual disturbances.

Gynecomastia has been associated with the use of calcium channel blockers.

8 STATISTICAL CONSIDERATIONS

8.1 General Design Issues

The study is designed as a randomized Phase 3, 2-arm, double-blind, parallel group trial with subjects randomized to Isradipine IR 5 mg or matching placebo twice daily.

Primary efficacy analysis will be performed after all subjects complete 36 months on their randomized treatment assignment. We expect that nearly all subjects will require symptomatic therapy (e.g., levodopa or dopamine agonist) prior to the end of the 36

months study; if so they will still continue on their randomized treatment assignment in conjunction with the symptomatic therapy. In that case the primary statistical analysis will be based on UPDRS assessed in the medications ON state (based on the subject/ investigator defined BEST ON, approximately 1 hour after dose of symptomatic therapy).

Primary efficacy variable

The primary efficacy measure is the change in the total UPDRS score in the active treatment arm versus placebo between the baseline and 36 months. In order to provide assurance that any differences between the treatment groups in the primary outcome measure are not due to differences in the usages of symptomatic medication, current and cumulative dosages of symptomatic medication at the 36-month visit will also be compared, using accepted levodopa dose equivalency formulas[1] We will also repeat our UPDRS analyses after stratification by medication status (dosage of symptomatic treatment calculated as the levodopa equivalent dose). We will also perform exploratory analyses along the lines suggested by Holford and Nutt[56], based on flexible models of both short term symptomatic effects and long-term disease-modifying effects of treatment.

Secondary efficacy measure

The study secondary objectives are to explore long-term efficacy of Isradipine IR 5 mg twice daily to slow progression of disability between the baseline and 36 months of treatment as measured by parameters that reflect long term disability in PD:

- 1) Motor function (characterized by UPDRS Part III OFF score, UPDRS ambulatory capacity subscore, time to initiation of symptomatic therapy, time to onset of motor complications, dose and utilization of symptomatic therapy)
- 2) Cognitive function as measured by MoCA
- 3) Global measures of disability as measured by modified Rankin score
- 4) Measures of functional status and quality of life (PDQ-39, modified Schwab and England, MDS-UPDRS Motor and Non-Motor Experience of Daily Living)

Interim tolerability analysis

An interim tolerability analysis will be performed after the first 60 subjects complete the titration period of the study (Visit 03 (Month 3). Tolerability will be defined as ability to achieve and maintain target daily dosage of study drug (10 mg) by the end of titration period. The tolerability threshold will be defined as more than 30% difference in the tolerability of the active treatment group relative to the placebo group. Only dosage reductions, discontinuations, and premature terminations due to intolerability will be included in the analysis, terminations for other reasons will not be included in this analysis. The study may be terminated if tolerability parameters are not met. These analyses will be conducted by the unblinded statistician and reported to the DSMB.

Interim analysis of the Pharmacokinetic (PK) data

An interim PK analysis will be performed (at steady-state) after the first 60 subjects who reach target daily dose of 10 mg complete the titration phase of the study to assure that serum concentrations fall within predicted range. C_{min} and C_{max} serum concentrations

will be analysed. Only data on the subjects who have reached 10mg dose of study drug (Isradipine IR or placebo) will be included in the interim analysis. Based on the data discussed in Section 2.1, we expect the C_{min} concentration to be 0.4±0.2 ng/ml (1 SD from the C_{min} mean). Thus C_{min} = 0.2 ng/ml should be established as the threshold of the therapeutic effect. In case mean C_{min} concentrations fall below 0.2 ng/ml, the following paradigm is proposed:

- 1) May validate the PK data by completing a full PK profile on a small sample of study subjects (N=6)
- 2) In case the AUC 0-12hr falls within the expected range (13.9± 6.1 ng/ml)(Holmes and Kutz 1993), the study will proceed as planned
- 3) In case AUC 0-12hr is below expected range the DSMB may seek independent assessment of the PK data by a clinical pharmacologist
- 4) In case the C_{min} values are below C_{floor} (0.25 nM (0.098 ng/ml)) – DSMB may consider an alternative dosing regimen

Interim futility and efficacy analysis

An interim analysis for futility and efficacy will be performed after primary outcome data are available for the first 168 subjects (50%) to enroll in the study. The study may be terminated for futility if the interim analysis shows that the conditional power of rejecting the null hypothesis in favor of a beneficial effect of isradipine is lower than 20% under any scenario that is consistent with the data accrued at that time. A two-sided P-value in favor of isradipine of less than 0.001 will be required to stop for efficacy at the interim analysis if the recruitment rate falls below that projected, the interim analysis may be brought forward and performed as soon as the first 30% of the subjects to enroll have completed (or terminated). In that case a second interim analysis for futility will be conducted on the first 75% of subjects to enroll.

These analyses will be conducted by the unblinded statistician and reported to the DSMB. The stringent alpha level for efficacy was chosen so as to have minimal effect on the final P-value, should the study run to completion. In addressing futility the DSMB will examine a range of possible treatment effects consistent with the data obtained in the study at the time of analysis.

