	
two-sided alpha level of 5%, the total sample size of 336 gives 80% power to detect a 4–point difference between the two groups, after allowance for 15% dropouts. This effect size is estimated to represent a 25% reduction in the rate of worsening after allowance for the benefit of symptomatic treatment. Secondary outcomes including measures of motor, cognitive and global disability and measures of functional changes and quality of life will be analyzed in the same way as the primary outcome. Measures of safety and tolerability, including ability to complete the study on the assigned dosage and the frequency, seriousness and severity of adverse events will be compared using Fisher’s exact test.

Interim Analyses	
Interim tolerability analysis
 
An interim tolerability analysis will be performed after the first 60 subjects complete the titration period (Visit 03, Month 3).
 
Interim analysis of the Pharmacokinetic (PK) data
 
An interim PK data analysis will be performed (at steady-state) after Cmin and Cmax PK data are available for the first 60 subjects who successfully complete titration to the target daily dose of 10 mg (Visit 03, Month 3).
 
Interim futility and efficacy analysis
 
An interim analysis for futility and efficacy will be performed after primary outcome data are available for the first 168 subjects (50%) to enroll in the study. If the recruitment rate falls below that projected, the interim analysis may be brought forward and performed as soon as the first 30% of the subjects to enroll have completed (or terminated). In that case, a second interim analysis for futility will be conducted on the first 75% of subjects to enroll.

Study Procedures	See the Schedule of Activities.
IND	The IND application # 113,513

STEADY-PD III Schedule of Activities

		Titration Phase				Maintenance Phase										Drug Taper					
Visits	Screen (SC)	Baseline (BL)	V01	V02	V03	V04	V05	V06	Phone Visit T01	V07	Phone Visit T02	V08	Phone Visit T03	V09	Phone Visit T04	V10 EOS D	V11 Post drug/ Final Visit	Premature Withdrawal (PW)	PW Follow-Up Visit ¹¹	Unscheduled Visit (U01, U02) ⁵	Symptomatic Tx Visit

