8.2 Outcomes

8.2.1 Primary Outcome

Efficacy:

Efficacy will be defined as the change in total UPDRS score between the baseline visit and month 36. Comparison will be made between active treatment arm and placebo. We expect that nearly all subjects will require symptomatic therapy (e.g. levodopa or dopamine agonist) prior to the end of the 36 months study. In that case UPDRS will be assessed in the medications ON state (based on the subject/ investigator defined BEST ON, approximately 1 hour after dose of symptomatic therapy).

Medications ON state was chosen based on the following rationale: if disease modifying effect of isradipine exists it will be sustained even in the medications ON state; the practical difficulty in withdrawing subjects; the persistent symptomatic benefit of symptomatic therapy even in the “defined medications OFF” state. In addition there are no pilot data on the longitudinal change of UPDRS in the medications OFF state over 36 months period in de novo population to allow power calculations.

Our primary efficacy analysis will use analysis of covariance applied to the change from baseline in the total UPDRS score. The baseline value will be entered into the model as a continuous variable, the assigned treatment and the enrolling Investigator will be entered as a stratification variable. The primary analysis will be based on the intent-to-treat principle and will include all subjects who have 36 month data. A two-sided test with $\alpha = 0.05$ will be used to declare statistical significance. Sensitivity analyses will be performed using data values imputed under various “missingness” mechanisms for the subjects who do not complete 36 months of follow-up. Consistency of results over study sites and with respect to major demographic and clinical baseline variables will be assessed descriptively and by appropriate tests of statistical interaction. We will also perform an exploratory analysis by achieved final dosage (0, 2.5, 5.0, 7.5 and 10.0) for the subjects assigned to active treatment.

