8.3 Sample Size and Accrual

The key issues in the determination of sample size are the variability of the primary outcome measure and the magnitude of the treatment effect one wishes to detect.

As regards the former, there are several sources of data regarding changes in total UPDRS in untreated patients to a two, three or four year point, generally following introduction of symptomatic therapy. Published sources include the CALM-PD study [57] and the Swedish selegiline study [58]. Unpublished data are also available from a long-term follow-up of patients originally enrolled in the PRECEPT study [59]. All these studies support a standard deviation of 12.0 units for the change in total UPDRS from baseline to 36 months. The same data suggest an average change in total UPDRS of around 4.0 points over this same time period. Of course this change is deceiving, as the change would like-

ly be much greater in the absence of symptomatic treatment. If we assume that treatment with levodopa or a dopaminergic agonist provides a “bonus” of 12 points, then the underlying true decline in function over this period would be around 16 points, a value broadly consistent with the rate of change in total UPDRS in subjects prior to treatment. We have chosen to power our study to detect a four point effect, representing an overall 25% reduction in the rate of progression. We believe that a difference of this magnitude would be sufficient to influence clinical practice and may suggest the likelihood of longer term benefit.

Using the above assumptions, a two-sided test with $\alpha = 0.05$ and $\beta = 0.8$ and making allowance for 15% dropouts the required sample size is 168 subjects per group or a total 336 subjects.

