C. *Sensitivity Analyses.* A variety of sensitivity analyses will be conducted to assess the robustness of the comparison between treatment groups.

- I. Non-parametric methods. Residual plots will be examined. In the event that these show outliers or pronounced non-normality, supplementary analyses will be performed after deletion of outliers and/or using appropriate non-parametric methods.
- II. Missing Data. Effects of missing data will be assessed (i) by multiple imputation and (ii) by “best case” and “worst-case” analysis and (iii) by the use of mixed models (which use intermediate study data to project final study outcomes when these are missing).
- III. Influence of Symptomatic Medication. Supplementary analyses of the final study outcomes will be conducted with current use of symptomatic medication (levodopa equivalents) added as an additional predictor variable. The purpose of this analysis is to assess whether any differences seen in the primary outcome variable could be attributed to differential use of symptomatic therapy between the treatment groups.

D. *Subgroup Analyses – Including Gender and Race/ Ethnicity*

Recognizing that the study will not have high power to detect treatment effects among subgroups, we will conduct exploratory analyses to check the consistency of treatment effects on the primary and secondary efficacy measures in relation to selected baseline characteristics, including gender and race/ ethnicity. The analysis will use two approaches (i) repeating the primary analysis for each subgroup (for example men and women; minority and non-minority) separately, (ii) inclusion of additional terms in the analysis of covariance model to represent the overall effect of the characteristic (do men progress faster than women?) and for the interaction of the treatment with the characteristic (does the effect of the treatment differ between men and women?). Results for each race/ethnic grouping will be tabulated separately.

5. Safety and Tolerability Analysis

A. *Primary Safety and Tolerability Outcomes.*

- I. The ability to complete the 36 months study on the originally assigned treatment dosage
- II. The proportion of subjects requiring dosage reductions secondary to intolerability
- III. The frequency of adverse events and serious adverse events
- IV. Laboratory and EKG abnormalities

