- (2) *Influence of Symptomatic Medication on the Primary Outcome.* Section 4C. III states that “Supplementary analyses of the final study outcome will be conducted with current use of symptomatic medication (levodopa equivalents) added as an additional predictor variable”. Since use of symptomatic medication is a post-randomization variable and may be determined in part by post-randomization values of the outcome variable, it should not be used as a predictor variable. Subjects who show a more rapid early decline may be more likely to receive symptomatic medication. This could result in an artefactual positive correlation between use of symptomatic medication and rapidity of disease progression which might distort the estimate of the randomized treatment. To avoid this artefact we will estimate the effect on the primary outcome of both current and cumulative dosages of symptomatic medication from a mixed model analysis using data from all study visits and which explicitly allows subjects to have differing underlying rates of disease progression. In essence this analysis uses each subject as his or her own control in estimating the influence of symptomatic medication on disease progression. It will be performed on the aggregate data from the final study data-base, prior to breaking the blind as to the randomized treatment. The estimated coefficients of the two LED variables (current and cumulative levodopa equivalent doses) will then be used to adjust each subject’s final UPDRS value to the projected value that the subject would have had if he or she had not received symptomatic medication. Since these projections will not use the randomized treatment, the treatment effect on the projected outcome variables can be estimated using the same model as the primary analysis, i.e. stratifying by site and including baseline UPDRS as a covariate. This analysis will have the correct alpha-level under the overall null hypothesis (no effect of isradipine relative to placebo on either disease progression or usage of symptomatic medication) irrespective of whether the relationship between these two outcome variables is modeled accurately. A member of the Steering Committee asked about the possible influence of body weight on the effect of LED. To assess this we conducted preliminary analyses on the aggregate study data with the raw values of current and cumulative LED divided by the subject’s weight giving LED per kilo of body weight. In addition to confirming the reality of the artefact described above the results were very similar to those using the original values of LED, so we propose not to adjust for body weight in this prespecified supplementary analysis.

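### Protocol 8.1 still repeats the UPDRS comparison within strata of symptomatic-medication dose, a post-randomization variable that the SAP clarification rejects as a predictor, so this check could attenuate a true slowing and does not isolate the medication effect

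*Protocol*

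**What the plan says.** Protocol 8.1, under the primary efficacy variable, seeks assurance that a UPDRS difference does not come from unequal use of symptomatic drugs. It plans to compare the arms on current and cumulative levodopa equivalent dose (LED) at month 36, and then adds: "We will also repeat our UPDRS analyses after stratification by medication status (dosage of symptomatic treatment calculated as the levodopa equivalent dose". It gives no cut points and does not say whether current or cumulative dose defines the strata.

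SAP 4.C.III approaches the same question differently: "Supplementary analyses of the final study outcomes will be conducted with current use of symptomatic medication (levodopa equivalents) added as an additional predictor variable". The sentence after it ties the purpose to differences in the primary outcome variable. The SAP itself contains no LED-stratified analysis.

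Item 2 of the SAP clarification of 28 December 2018 is headed as concerning the primary outcome and reverses 4.C.III. It reasons that symptomatic medication is determined after randomization, partly by how the outcome has evolved, and concludes that "it should not be used as a predictor variable". In its place it puts a mixed model fitted to all visits on pooled data before unblinding. The two LED coefficients project each subject's final UPDRS to a no-medication value, which is then analysed with the primary model. The clarification gives its scope as two aspects of the SAP. It does not mention Protocol 8.1, and it quotes 4.C.III with outcome in the singular.

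**The concern.** The documents themselves place LED downstream of disability. Protocol 6.3.12 bases the need for symptomatic treatment on disability. SAP section 7 treats dose as a surrogate for severity. Both documents list LED as a secondary outcome. If isradipine slows the disease, it should also lower LED.

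Within a stratum of equal LED the arms are then no longer comparable by randomization. A subject on isradipine who still reached a high dose will tend to have been a faster progressor than a placebo subject at that dose. This is the objection that the clarification raises against the covariate, and grouping the dose into strata does not remove it.

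The analysis exists to guide how the primary result is read. A reduced stratified estimate could be taken to mean that symptomatic therapy accounts for the effect, when the reduction may come from the conditioning. There is also a conduct problem: running the analysis contradicts the SAP's reasoning, and dropping it without comment departs from the Protocol.

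**Working it through.** **The plan's own figures.** Inputs from Protocol 8.3: "We have chosen to power our study to detect a four point effect", an SD of 12.0 and 15% dropout. With two-sided alpha 0.05 and 80% power:

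- n per arm = 2 × (1.960 + 0.842)² × 12² / 4² ≈ 141.3, rounded up to 142.
- 142 / 0.85 ≈ 167.1, rounded up to 168 per arm, 336 in total, as stated.
- With 168 × 0.85 = 142.8 completers per arm, power is 80.4%.
- Detectable LED difference (SAP section 7, SD 277): 2.802 × 277 × √(2/142.8) ≈ 91.8, against 92 stated.

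LED enters none of the sample-size figures for the primary comparison.

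**Model for the conditioning.** Slowing is written as a positive number.

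- Underlying progression P is 4 points lower on isradipine.
- LED rises with P, with within-arm correlation r and SD 277 (SAP section 7).
- Observed ON score Y = P − c × LED, where c is symptomatic benefit per LED unit.
- Assumed, because the documents do not give them: r, the SD of P, and a benefit linear in LED. The 12-point bonus (SAP section 7) and mean LED of 390 are the documents' own. Spreading the bonus linearly over dose is an assumption.

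The effect on LED is 4 × r × 277 / SD(P). Hence:

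- Unadjusted effect on Y = 4 × (1 − c × r × 277 / SD(P)).
- Effect at fixed LED: the slope of P on LED within arm is r × SD(P) / 277, so the effect is 4 − 4 × r² = 4 × (1 − r²), whatever c is.

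**Results with SD(P) = 10.** The values of c are 0, 0.01, 6/390 = 0.0154 and 12/390 = 0.0308, so c × 277 / 10 is 0, 0.277, 0.426 and 0.852.

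| r | At fixed LED | Unadjusted, c = 0 | Unadjusted, c = 0.01 | Unadjusted, 6 points at 390 | Unadjusted, 12 points at 390 |
|---|---|---|---|---|---|
| 0.3 | 3.64 | 4.00 | 3.67 | 3.49 | 2.98 |
| 0.5 | 3.00 | 4.00 | 3.45 | 3.15 | 2.30 |
| 0.7 | 2.04 | 4.00 | 3.22 | 2.81 | 1.61 |

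The estimate at fixed LED is below the unadjusted one only when r exceeds c × 277 / SD(P). For SD(P) = 10 the switch points are 0, 0.28, 0.43 and 0.85. With SD(P) = 12 they are 0.36 for the 6-point benefit and 0.71 for the 12-point benefit. With SD(P) = 6 they are 0.71 and above 1, so in the last case no reversal back occurs.

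**Strata instead of a covariate.** Simulation with SD(P) = 10 and no dose-dependent benefit gives 3.74, 3.18 and 2.46 for LED tertiles and 3.69, 3.15 and 2.35 for quartiles, at r = 0.3, 0.5 and 0.7. With the 12-point benefit, quartiles give 3.55, 2.87 and 2.00. Coarse strata therefore condition slightly less or about as much as the covariate does.

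**The case against.** The best defence is that the Protocol sentence is simply stale. Version 6.0 dates from August 2016. The SAP carries no LED-stratified analysis. The covariate that served the same purpose was replaced in December 2018 by a better method, with an explicit reason. The sponsor probably means to run the projection only. That is a fair guess at intent, but no text says so, and the clarification confines itself to the SAP.

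It is also true that the analysis is supplementary. The primary ANCOVA contains no LED term, so the main test is safe. This limits the weight of the point without removing it, since the stratified repeat is meant to bear on how the main result is interpreted.

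A reader might infer from the plural in 4.C.III that the SAP still adjusts the secondary outcomes for LED. The documents do not support that as a statement of fact. The section names no secondary outcome, its purpose sentence concerns only the primary, and the clarification's reason applies to any outcome. What can be said is that the replacement is given for the primary outcome alone, which leaves the status of 4.C.III for the others unclear.

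**Conclusion.** The point holds as an unreconciled conflict between Protocol 8.1 and the SAP clarification, over a supplementary analysis that cannot separate a treatment effect from an effect of symptomatic medication. In a linear model, conditioning on LED turns an underlying slowing of 4 points into 3.6, 3.0 or 2.0 points at r = 0.3, 0.5 or 0.7. Strata give similar values. The correlation is assumed.

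A reader might go further and infer that a real slowing would necessarily look smaller than the primary estimate. That does not follow. If the 12-point bonus is linear in dose and SD(P) is 10, the estimate at fixed LED is larger than the unadjusted one at all three values of r (3.64, 3.00, 2.04 against 2.98, 2.30, 1.61), though still short of 4. The clarification says that the artefact was borne out in the aggregate data, which favours attenuation, but it gives no size and says only that the treatment estimate might be distorted. The supportable wording is that the effect could be attenuated.

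In this model, if there is no effect on progression the conditioned estimate is also zero. The issue is therefore the interpretation of a real effect and not a false positive. The clarification also advises against the predictor in terms of should not, which is weaker than a prohibition.

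**What to change.** Before the blind is broken, add a short statement, in the SAP clarification or a protocol note, that:

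- the LED-stratified repeat in Protocol 8.1 is withdrawn and replaced by the clarification's projection analysis; or, if a stratified table is kept, it is descriptive, with stated cut points and no treatment-effect P-value;
- the LED covariate in SAP 4.C.III is withdrawn for all outcomes;
- the between-arm comparison of current and cumulative LED is kept.

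Extending the projection to secondary scores is optional. It would be hard for the MDS-UPDRS, which is scheduled only at baseline, months 12, 24 and 36, and the symptomatic treatment and withdrawal visits, leaving few points per subject.

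The cost is a few sentences and the loss of one familiar supplementary table. The primary ANCOVA, alpha and N = 336 do not change.
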